- The following protocol deviations may be considered major with the implication of data exclusion from the PP analysis population:
- A premature withdrawal, except for those who dropped out due to an insufficient treatment effect;
 - Missing primary variable value;
 - Violation of one or more inclusion/exclusion criteria (ineligibility);
 - Error in treatment assignment;
 - Use of excluded medication;
 - Use of Dilapan-S® or Foley catheter though contraindicated;
 - The subject does not deliver during the hospitalization in the study center.

These criteria will be updated and detailed in the SAP after the data review and before the clinical database has been frozen, without knowing the treatment assignment.

The PP population will be analysed according to their actual study treatment used (i.e. “as treated”). The PP population is the primary efficacy population.

Subject Disposition

All subjects screened and randomised will be accounted for. All post-randomisation discontinuations will be summarised by time of, and reason for, discontinuation. The number of subject screened and not randomised will be presented with the main reason for their non-inclusion.

The number of patients who were randomised will be reported. The patients with wrong assignment to treatment will be summarised by treatment and listed.

Patient Demographics and other Baseline Characteristics

Summary statistics of demographics, medical history, and other baseline characteristics will be presented by treatment group. The ARS population will be used.

Primary Efficacy Variable Analysis

Primary Efficacy Endpoint

The primary efficacy endpoint is the rate of overall vaginal delivery.

Statistical Hypothesis, Model and Method of Analysis

The primary hypothesis testing consists of simultaneous/combined tests for non-inferiority and superiority - a useful strategy proposed for a confirmatory phase III clinical trials [1] and accepted by EMA in 2000 (CPMP/EWP/482/99, PtC on switching between superiority and non-inferiority), provided that the non-inferiority margin has been defined in advance in the study protocol.

Statistical inference involves testing the hypotheses regarding the difference in proportions with a vaginal delivery between the Dilapan group and the foley group. For the non-inferiority test, this can be expressed as $H_{N0}: PD \leq PF - \delta$.

against the alternative $H_{NA}: PD > PF - \delta$.

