Where PD and PF denote population proportions for Dilapan and foley group, respectively, and $\delta > 0$ is a non-inferiority margin. This type of test is called a test of non-inferiority.

If the purpose of the test is to prove the superiority of Dilapan to foley superiority, then

$H_{S0}: PD \leq PF$

will be tested against the alternative

$H_{SA}: PD > PF$

This setting generates the usual one-sided test of superiority.

These two tests can be performed simultaneously by employing the closed testing procedure (CTP) while controlling the overall type I error at the level α . In this special case, the resulting procedure is as follows:

1. First, the test of non-inferiority should be performed at the $\alpha=0.025$, one-sided. If H_{N0} is rejected, the test of superiority should be done at the $\alpha=0.025$, one-sided. Otherwise we can conclude that not even non-inferiority of Dilapan-S can be drawn.

2. In the test of superiority at the second step, if H_{S0} is rejected at the $\alpha=0.025$, one-sided, we should conclude that Dilapan-S is superior to the control. Otherwise non-inferiority can be concluded. It can be shown that this testing procedure is equivalent to a $(1-2\alpha)$ 2-sided confidence interval (CI) approach. The CI approach will be used in accordance with ICH E9 recommendations. The 95% 2-sided CI for Dilapan-S – Foley catheter difference will be calculated. A decision will be made as follows:

1. If the 95% CI is completely on the right side to the zero point, it will be concluded that Dilapan is superior over foley.

2. Otherwise, if the 95% CI is completely on the right side to the non-inferiority margin, it will be concluded that Dilapan-S is non-inferior to Foley catheter.

3. Otherwise no conclusion will be drawn.

For the non-inferiority test, the PP analysis population is often chosen as the primary population. To control type I error at the pre-specified level, the same population should be used for the superiority test within the frame of the closed testing procedure. As a result, PP set will be used for both tests as the primary analysis population. However, to demonstrate robustness to the alternative choice, the primary endpoint will also be performed using the ITT analysis population. The ITT analysis for the primary efficacy endpoint will be used to support the primary analysis using the PP population.

Secondary Variables Analysis

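### Superiority is judged on the per-protocol set for a type I error reason that does not hold, while the as-randomised ITT analysis is only supportive

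*Combined protocol and SAP*

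**What the plan says.** Under Statistical Hypothesis, Model and Method of Analysis (section 14), non-inferiority is tested first at one-sided 0.025 and, if it is shown, superiority at the same level. The plan states "It can be shown that this testing procedure is equivalent to a" two-sided confidence interval, and reads both conclusions from one 95% interval: superior if it lies above zero, non-inferior if it lies above the margin, otherwise no conclusion.

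On the population it says "To control type I error at the pre-specified level, the same population should be used for the superiority test", within the closed testing procedure, and concludes "As a result, PP set will be used for both tests as the primary analysis population". The as-randomised analysis has a secondary role: "The ITT analysis for the primary efficacy endpoint will be used to support the primary analysis using the PP population".

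The Per Protocol Population subsection lists deviations that may lead to exclusion. They include "A premature withdrawal, except for those who dropped out due to an insufficient treatment effect", use of excluded medication, "Error in treatment assignment", and "The subject does not deliver during the hospitalization in the study center". It also says "The PP population will be analysed according to their actual study treatment used".

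Elsewhere, the data-collection text in section 4 and the opening of section 14 each say, without qualification, that analysis is by intent to treat. In the ITT subsection, the sentence that should introduce the uses of that set is followed by the PP exclusion list, apparently a misplaced block.

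**The concern.** There are three problems.

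- **The reason is wrong.** Type I error control is given as the ground for testing superiority on PP. The order of testing already controls the error, so that ground falls away.
- **The choice has a cost.** Several possible PP exclusions happen after randomisation, and staff and patients know the device. If such events depend on the device and relate to mode of delivery, the PP comparison is no longer a randomised one. The decision rule contains no step at which the ITT result could stop a superiority claim.
- **The text conflicts.** Two places promise intent-to-treat analysis, and the detailed section makes PP primary. The list in the ITT subsection does not say what ITT is for. Assignment errors are a possible PP exclusion, yet PP is also to be grouped by device used, so the handling of a woman given the other device is not settled.

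At stake is whether a published claim of superiority would rest on the randomised comparison.

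**Working it through.** **1. Inputs and the plan's own figure.** From Sample Size Calculation: 71% Foley, 76% Dilapan-S, margin 10 points, one-sided 0.025, power 90%, 13% outside the primary set.

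n per arm = (1.960 + 1.282)² × (0.71×0.29 + 0.76×0.24) / (0.05 + 0.10)² = 10.51 × 0.3883 / 0.0225 ≈ 181.4, rounded up to 182. Then 364 / 0.87 = 418.4, or 419, against 420 stated. The plan's figures are reproduced. About 420/2 = 210 are randomised per arm and 210 × 0.87 ≈ 183 are in PP.

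**2. Does error control need one population?** Let N be the non-inferiority null on PP and S the superiority null on ITT.

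- If N is true, any false claim requires N to be rejected first: probability at most 0.025.
- If N is false and S is true, only the superiority test can err: probability at most 0.025.

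In closed-testing terms, the PP non-inferiority test is a valid level-0.025 test of the intersection of N and S. A shared population gives nested hypotheses and the single-interval rule, not the error control. Simulation (1,000,000 trials, Wald intervals) agrees. With both arms at 71% and no selection, false superiority after PP non-inferiority is 2.57% on ITT and 2.58% on PP. With a PP difference of -10 points and an ITT difference of 0, so that both nulls are true, false non-inferiority is 2.51% and false superiority on ITT 1.58%.

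**3. Can the rule declare superiority when ITT does not?** Lower limit = difference - 1.96 × √[p₁(1-p₁)/n₁ + p₀(1-p₀)/n₀].

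- PP 147/183 v 130/183: difference 9.29 points, SE 4.46, lower limit 9.29 - 8.74 = +0.55. Superior.
- Add 27 excluded women per arm, 19 of 27 delivering vaginally in each. ITT is 166/210 v 149/210: difference 8.10 points, SE 4.21, lower limit 8.10 - 8.25 = -0.15. Not superior.

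**4. How far could the error move?** The gaps are assumptions; the documents give none. Both arms are at 71% as randomised and 13% are excluded from PP. Excluded Foley women are at 71%, and excluded Dilapan-S women are d points lower. The retained Dilapan-S rate is then (0.71 - 0.13 × (0.71 - d)) / 0.87, which shifts the PP difference by 0.13d/0.87. For d = 10 points the shift is 1.49 points. With a PP standard error of about 4.7 points that is 0.32 standard errors, and the chance of exceeding 1.96 - 0.32 = 1.64 is about 5.0%, in line with the simulation.

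Simulated percentages of trials, with superiority counted only after PP non-inferiority:

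| d (points) | False superiority, PP | False superiority, ITT, all outcomes known | False superiority, ITT, half of excluded women without outcome | PP superior, ITT not (all known) |
|---|---|---|---|---|
| -10 | 1.2 | 2.5-2.6 | - | - |
| 0 | 2.6 | 2.5-2.6 | - | 0.9 |
| 5 | 3.7 | 2.5-2.6 | 3.0-3.1 | 1.7 |
| 10 | 5.1 | 2.5-2.6 | 3.5-3.6 | 2.9 |
| 20 | 9.5 | 2.5-2.6 | 4.8-5.0 | 7.0 |

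If no excluded woman has an outcome, ITT equals PP. A fixed split of 183 kept and 27 excluded gives nearly the same results as binomial exclusion.

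**5. Non-inferiority under the same selection.** At the margin (61% v 71% as randomised), false non-inferiority on PP is about 3.5%, 4.9% or 8.8% for d = 5, 10, 20. On ITT it is 2.4-2.5% with all outcomes known, and about 3.0%, 3.5% or 4.7% with half missing.

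**The case against.** The best defence is that the disputed sentence is set within the closed testing procedure, and that reading one interval against both -10 and 0 does need one population. That is true of the single-interval rule, but it is not a reason based on type I error.

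The example in step 3 shows no bias. The excluded women do equally well in both arms, and with no gap, discordance is almost symmetric: PP alone superior in 0.86% of trials, ITT alone in 0.84%. This is right. The example shows only what the rule permits.

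The magnitudes treat the whole 13% as selectively excluded with outcomes known. The plan's 13% also covers drop-out and loss to follow-up, and eligibility violations are baseline facts. If only 5% are selectively excluded, false superiority on PP is 3.3% or 4.3% at gaps of 10 or 20 points. This also stands, and the table should be read with it in mind.

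The plan has real safeguards. Classification is blinded and documented, PP criteria are settled before database freeze without knowledge of assignment, and statisticians are masked. Withdrawals for insufficient effect stay in PP, assignment errors may be excluded so that regrouping may be rare, and an as-randomised ITT analysis of the primary endpoint is planned. These prevent deliberate selection. They do not restore comparability if the exclusion events themselves depend on the device, and none of them changes the decision rule.

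Finally, superiority is not the powered objective; its power at +5 points is about 19%. That limits the reach of the problem but does not justify the rule.

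**Conclusion.** The concern holds and should be fixed. The stated reason for testing superiority on PP is incorrect, the rule can declare superiority when the as-randomised interval includes zero, and the intent-to-treat statements contradict the choice of PP as primary. PP as the primary set for non-inferiority is not disputed, and the powered objective keeps its sample size.

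The size and direction of any bias are unknown. The range of 1.2% to 9.5% in step 4 assumes 13% selective exclusion and gaps from 10 points in favour of excluded Dilapan-S women to 20 points against them. The protection from ITT is also limited: the ITT definition and the missing-data subsection drop women without a primary outcome, so ITT helps only as far as PP-excluded women have one. The plan expects missing outcomes to be very rare.

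**What to change.** Amend section 4 and section 14 as follows.

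1. **Two steps, one 95% interval each.** Step 1, PP: if the lower limit is above -10 points, conclude non-inferiority and go on; otherwise draw no conclusion. Step 2, ITT as randomised: if the lower limit is above 0, conclude superiority; otherwise non-inferiority only. Delete the sentence that ties type I error control to a common population, and the single-interval equivalence statement.
2. **Reconcile the populations.** Make both intent-to-treat sentences match this rule. Replace the misplaced list in the ITT subsection with the actual uses: the superiority test and the supportive non-inferiority interval.
3. **PP grouping.** Analyse PP by randomised arm, excluding rather than moving women who received the other device.
4. **ITT non-inferiority interval.** Report it beside the PP interval, because moving superiority to ITT does not address step 5 of the working.
5. **Missing outcomes.** Fix now, rather than after the clinical data are known, a sensitivity analysis of superiority in all randomised women. Count a missing outcome as no vaginal delivery on Dilapan-S and as vaginal delivery on Foley, with a tipping-point table for the cases between.

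Items 3 and 5 are inexpensive additions; the main point does not depend on them.

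**Cost:** wording and a little analysis. The figures 182, 364 and 420 stand, and non-inferiority power on PP stays at about 90%. Superiority power at +5 points is about 19% on PP and about 14-22% on ITT, depending on the effect in excluded women and how many have an outcome. Requiring non-inferiority on both sets is not proposed; it would lower that power from 90.2% to 86.4-89.4%.

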The study will be explained as in the consent form and if agreed, subjects will elect either to or not to participate in the study after all risks and benefits are explained. Data to be collected will consist of age gravida/para, gestational age, BMI, time of date of intervention, time date of delivery, mode of delivery, bishop score at admission, bishop score after 12 hrs. of intervention, time and date of rupture of membranes, vaginal delivery within 24 hrs., hospital length of stay, other intrapartum and obstetrical interventions, complications in labor and delivery including but not limited to infections, hemorrhage, fetal decelerations and subject satisfaction. Data will be abstracted from subjects medical records as well as from direct interview with the subject. We will also collect basic neonatal data including birth weight, Apgar scores, rate of admission to neonatal intensive care unit, infections, and other neonatal complications. If elected to participate consents will be obtained and stored in subject chart. A copy of the consent will be given to the subject. Subjects will be consented in either English or Spanish by research personnel familiar with the language. Randomization will be done at time of consents. The study's time frame inclusive will be from 2016 till 2018. Data will be analyzed as per intent to treat.

Sample Size Calculation

The sample size will be calculated for the non-inferiority test.

The significance level of the test is targeted at 0.025, one-sided.

The rate of overall vaginal delivery is 71% and 76% for Foley catheter and Dilapan-S® , respectively. Higher rates are better.

The non-inferiority margin is $\delta=10\%$. It is defined as the largest treatment difference of no clinical importance.

The treatment allocation ratio will be 1:1.

The power of the non-inferiority test to be achieved is 90%.

Based on the above assumptions, the sample size would be 182 evaluable subjects in either treatment group, i.e. 364 evaluable subjects in total. Assuming that 13% of patients will not qualify for the primary analysis set (due to protocol deviation or considered as drop-out of loss to follow up), 420 patients are to be enrolled into this study.

5. Sub-Study Procedures: Not applicable.

6. Criteria for Inclusion of Subjects:

- Pregnant woman scheduled for induction of labor
- Age between 18 and 45 years
- Understanding and capable to sign informed consent
- Singleton pregnancy
- Gestational age ≥ 37 ^{0/7}weeks

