Rate of vaginal deliveries within 24 hours, rate of vaginal deliveries within 36 hours, rate of spontaneous vaginal deliveries, rate of operative vaginal deliveries and rate of caesarean sections will be analysed using similar statistical methods as described above for the primary endpoint, except for the definition of the non-inferiority margin and for the non-inferiority test. The 95% 2-sided CIs will be calculated for the treatment differences.

Time to reach active stage of labour defined as ≥ 6 cm (mins) will be analysed using survival analysis methods. Detailed methodology including set-up of censored values will be described in the final SAP. Change in Bishop score from baseline will be summarised by treatment group.

All rates above, time to reach active stage of labour and Bishop score are related to the secondary objectives and simultaneously, they are supportive measurements related to the primary objective. Patient satisfaction associated with the device used for cervical ripening (Patient Satisfaction Survey, question No. 12) will be evaluated as a secondary objective. Counts and proportions in all categories will be presented by treatment group. The location shift in response categories between the two treatment groups will be calculated and tested at the $\alpha = 0.05$ level of significance, two-sided.

Exploratory Variables Analysis

Exploratory variables will be summarised by treatment group.

Safety Variables Analysis

Safety variables will be summarised by treatment group.

Procedure for Accounting for Missing Data

Study subjects with missing primary variable will be evaluable neither for the ITT nor for the PPS population.

Missing primary variable data is expected to be very rare. If not, a different procedure may be refined in the SAP (e.g. a conservative imputation technique or sensitivity analyses) with the knowledge of the clinical data.

Procedure for Protocol Deviations

All protocol deviations will be listed by treatment group. Study subjects with a major protocol deviation will be excluded from the PPS analysis which makes demonstration of lack of sensitivity to protocol deviations possible (robustness).

Procedures for Deviations from the Original Statistical Plan

The SAP will contain more detailed description of the statistical analysis. If a need to change procedures of the analysis arises, an appropriate SAP update will be made. Major changes will require a protocol amendment.

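### Do the primary CI rule carried over to caesarean and operative delivery, and the missing minus sign in the non-inferiority rule, lead to wrong-signed conclusions?

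*Combined protocol and SAP*

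**What the plan says.** Section 4, Sample Size Calculation, fixes the direction for the primary endpoint. It states "The rate of overall vaginal delivery is 71% and 76% for Foley catheter and Dilapan-S® , respectively" and adds directly afterwards "Higher rates are better". The margin is 10 percentage points, and the test level is given as "The significance level of the test is targeted at 0.025, one-sided".

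Section 14, Primary Efficacy Variable Analysis, frames the hypotheses as a comparison of the proportions delivering vaginally. The non-inferiority null is PD ≤ PF − δ, with δ positive. Superiority is tested only once that null has been rejected, and the CI approach is described as equivalent to this two-step procedure. The first decision rule is "If the 95% CI is completely on the right side to the zero point, it will be concluded that Dilapan is superior over foley". The second begins "Otherwise, if the 95% CI is completely on the right side to the non-inferiority margin" and leads to a claim of non-inferiority. In all other cases no conclusion is drawn.

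Section 14, Secondary Variables Analysis, covers five rates: vaginal delivery within 24 hours and within 36 hours, spontaneous vaginal delivery, operative vaginal delivery and caesarean section. It says "rate of operative vaginal deliveries and rate of caesarean sections will be analysed using similar statistical methods as described above for the primary endpoint" and leaves out the margin and the non-inferiority test. The next sentence provides two-sided 95% CIs for the treatment differences. No direction of benefit and no decision wording is given for any of the five.

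**The concern.** The primary decision rule runs one way: a CI to the right of zero favours Dilapan-S. That is correct for vaginal delivery. For caesarean section a higher rate is worse, and the secondary section does not say that the direction reverses. Followed to the letter, the rule would label an excess of caesareans as superiority and a reduction as no conclusion. If every analysed woman delivers either vaginally or by caesarean, the caesarean rate is one minus the primary endpoint. The same women could then yield opposite verdicts on two versions of one outcome. Operative vaginal delivery also has no stated direction.

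Separately, δ is defined as positive, and the second decision rule compares the CI with the margin without a minus sign. Taken literally the boundary is +10 points. Any CI above +10 is also above zero, so the first rule would already have applied and non-inferiority could never be declared. That would touch the main claim of the trial.

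**Working it through.** **Inputs.** From section 4: vaginal delivery 71% (Foley) and 76% (Dilapan-S), margin 10 points, one-sided 0.025, power 90%, 182 evaluable per arm. From section 14: difference taken as Dilapan-S minus Foley, null PD ≤ PF − δ. All other rates and counts below are illustrative assumptions. Standard errors are unpooled, with a normal approximation.

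**1. The plan's own sample size.** With the boundary at −10 points, the distance from the planning difference is 0.05 + 0.10 = 0.15.

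n = (1.960 + 1.282)² × (0.76 × 0.24 + 0.71 × 0.29) / 0.15² = 10.507 × 0.3883 / 0.0225 = 181.3, so 182 per arm and 364 in total, as stated.

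**2. Sign of the margin in the second rule.** SE = √(0.3883/182) = 0.0462.

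- Boundary −10: P(lower limit > −0.10) = Φ(0.15/0.0462 − 1.96) = 0.901, the planned power.
- Boundary +10: P(lower limit > +0.10) = Φ(−0.05/0.0462 − 1.96) = 0.001. Even these CIs would already have met the first rule.

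With a +10 boundary the planning difference of +5 lies on the wrong side, so no sample size could give 90% power. The 182 is consistent only with −10, which is also what the null hypothesis says.

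**3. Caesarean, rule applied literally.** Assume vaginal delivery of 82% versus 71%.

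- SE = √((0.82 × 0.18 + 0.71 × 0.29)/182) = 0.0441.
- Vaginal delivery: 0.11 ± 1.96 × 0.0441 = +2.4 to +19.6 points (superior).
- Caesarean in the same women, 18% versus 29%: −19.6 to −2.4 (no conclusion, read literally).
- Arms exchanged, caesarean 29% versus 18%: +2.4 to +19.6 (superior, read literally).

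If the true caesarean rates were 34% versus 29%, the literal rule would say superior with probability 17.6%; at 39% versus 29%, 52.6%. So the literal reading is clearly absurd, and the question is whether the plan prescribes it.

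**4. What the text transfers.** Three features speak against a literal transfer.

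- The primary procedure reaches the superiority test only through the non-inferiority test. The secondary section removes that test, so the procedure cannot carry over unchanged.
- The output it names is a two-sided CI for each difference. That interval is the same whichever direction counts as benefit.
- The direction is attached to vaginal delivery in sections 4 and 14, and section 13 equates caesarean with failed induction, a cost to be reduced.

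**5. Operative vaginal delivery.** These deliveries count as successes in the primary endpoint, and no section says that fewer are better. Assume, per 182 women (Dilapan-S versus Foley), spontaneous 111 versus 111, operative 36 versus 18, caesarean 35 versus 53.

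- Operative: 36/182 − 18/182 = +9.9 points, CI +2.7 to +17.1.
- All vaginal: 147/182 − 129/182 = +9.9 points, CI +1.2 to +18.6.

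Here the operative rate rises because caesareans fall. A lower-is-better rule would count this against Dilapan-S although overall vaginal delivery improves.

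**6. Remaining rates.** The 24-hour, 36-hour and spontaneous vaginal delivery rates are vaginal-delivery rates, so the primary direction fits them.

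**The case for a change.** The case for a change is that the secondary section excepts two items and not the superiority rule, so a strict reader may hold that the rule was carried over. The section calls these rates supportive of the primary objective, so they will be read beside it. The trial is open-label, and settling a direction after the data are seen is better avoided. The plan also promises to report the originally planned analysis after any change, so loose wording could persist. The correction would cost a line or two.

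Part of this stands. The direction for caesarean is not written down, and the minus sign is missing from the operative sentence for the primary endpoint. But neither leaves the analyst a real choice. The caesarean direction follows from the primary endpoint, of which it is the complement when every analysed woman delivers one way or the other; non-delivery during the study hospitalisation is listed as a possible ground for exclusion from the per-protocol set. Reporting caesarean as well is then redundant but harmless. The originally planned output is a two-sided CI, which carries no sign error to persist. For operative vaginal delivery, a stated direction would bring in a preference that the documents do not contain.

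**Conclusion.** The concern does not call for a change. The arithmetic behind it is right, but a wrong-signed superiority verdict on caesarean is an inference from the word similar; the plan states no such rule. Of the five secondary rates, three run in the primary direction, one (operative vaginal delivery) has no fixed direction, and only caesarean is clearly reversed, where any analyst would read the two-sided CI the right way round. The missing minus sign is a clerical slip, settled by the null hypothesis, by the stated equivalence of the CI approach and by the 182 per arm. The more detailed SAP that the plan announces is the natural place for such wording.

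The effect on the primary hypotheses, the margin, the sample size and the 90% power is nil. This rests on reading the non-inferiority boundary at −10 points, as the null hypothesis has it, and, for the mirror-image CIs, on every analysed woman delivering either vaginally or by caesarean.

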3. Concise Summary of Project: Primary outcome will be to compare the efficacy of achieving a vaginal delivery using the synthetic osmotic cervical dilator Dilapan-S® versus Foley catheter for cervical ripening prior to induction of labor. Secondary outcomes will be to evaluate the efficacy of Dilapan-S® versus Foley catheter on other clinical outcomes such as vaginal delivery rate within 24 and 36 hours post insertion, time to reach active stage of labor defined as ≥ 6 cm, change in Bishop score, rate of spontaneous and operative vaginal delivery, rate of caesarean sections and patient satisfaction. Randomization will be performed using a computer generated random list of numbers assigning subjects to the 2 groups of the study. This list of random number assignments will be kept secure in an opaque envelope until the end of the study.

4. Study Procedures:

After institutional review approval, pregnant women that are scheduled for induction of labor will be approached by principal investigator or any of the co-investigators for participation in the study in a private subject room in labor and delivery unit. Prospective subjects presenting for induction of labor in labor and delivery, and willing to participate in the study will be evaluated for their eligibility including, including their bishop score. The latter will be obtained from the subject chart after the initial pelvic exam which is standard of care for these subjects in our unit. After obtaining informed consent, subjects will be randomized.

Group assigned to receive synthetic osmotic cervical dilator:

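### Change in Bishop score is listed as a Dilapan-S versus Foley outcome, but only a by-arm summary is planned, with no between-arm estimate, confidence interval or covariate adjustment for the admission score

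*Combined protocol and SAP*

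**What the plan says.** Section 3 (Concise Summary of Project) sets the purpose: "Secondary outcomes will be to evaluate the efficacy of Dilapan-S® versus Foley catheter on other clinical outcomes". The list that follows includes "change in Bishop score, rate of spontaneous and operative vaginal delivery".

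Section 14, Secondary Variables Analysis, gives the method: "Change in Bishop score from baseline will be summarised by treatment group". It also assigns a role to this outcome, saying that time to active labour and "Bishop score are related to the secondary objectives and simultaneously, they are supportive measurements related to the primary objective".

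The other secondary outcomes are treated as follows in the same subsection:

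- Delivery rates: "The 95% 2-sided CIs will be calculated for the treatment differences".
- Time to 6 cm: survival methods, with the remainder deferred: "Detailed methodology including set-up of censored values will be described in the final SAP".
- Satisfaction: "The location shift in response categories between the two treatment groups will be calculated and tested at the" two-sided 0.05 level.

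The data list in Section 4 includes "bishop score at admission, bishop score after 12 hrs. of intervention", and it also includes parity.

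**The concern.** The trial compares two devices for ripening the cervix, and the Bishop score is the recorded measure of cervical status before and after their use. The plan declares the change in that score to be comparative and supportive of the primary objective. It then gives the score the same descriptive treatment as the exploratory and safety variables, without saying why.

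As the text stands, the report would show two arm summaries and no prespecified comparative result on ripening. Any contrast would have to be chosen later. The trial is open-label, and the plan itself says that the resulting risk of influencing the results must be discussed, so a contrast fixed in advance is worth more than one chosen after data review.

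There is a second, smaller issue. If a contrast is later built from the planned summaries, it will be a difference in raw mean changes. That subtracts the full admission score whatever its correlation with the later score, and in general it is less precise than adjusting for the admission score as a covariate.

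**Working it through.** **1. The plan's own figure.** The documents give no figure for the Bishop score. The only size to work from is the primary-endpoint sample size in Section 4: 71% versus 76%, margin 10 points, one-sided 0.025, power 90%.

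n per arm = (0.71×0.29 + 0.76×0.24) × (1.960 + 1.282)² / (0.05 + 0.10)² = 0.3883 × 10.51 / 0.0225 = 181.3, rounded up to 182. This matches the plan. Allowing for 13% non-evaluable, 364/0.87 = 418.4, against 420 stated. The Bishop point does not depend on these figures except for the number of women available.

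**2. Is a between-arm Bishop estimate worth having at this size?** The 95% CI half-width is 1.96 × SD × √(2/182) = 0.205 × SD, where SD is that of the analysed quantity (for ANCOVA, the residual SD). The documents give no SD, so I assume a range.

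| Assumed SD (points) | Half-width | Difference detectable with 90% power, two-sided 0.05 |
|---|---|---|
| 1.5 | 0.31 | 0.51 |
| 2 | 0.41 | 0.68 |
| 3 | 0.62 | 1.02 |

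The estimate is usefully precise with no change in sample size. The figures assume that all 182 women per arm have both scores, and fewer will widen the interval.

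**3. What does covariate adjustment add over raw change?** Let the follow-up SD be 1, the baseline SD be k, and the baseline–follow-up correlation be r. Both k and r are assumptions, taken as equal in the two arms.

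- Variance of change: 1 + k² − 2rk
- Residual variance after adjustment: 1 − r²
- Ratio (adjusted/change): (1 − r²)/(1 + k² − 2rk)

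| k | r = 0.2 | r = 0.4 | r = 0.6 |
|---|---|---|---|
| 1.0 | 0.60 | 0.70 | 0.80 |
| 0.7 | 0.79 | 0.90 | 0.98 |
| 0.5 | 0.91 | 0.99 | 0.98 |

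The two variances differ by (1 + k² − 2rk) − (1 − r²) = (k − r)², which is never negative. In large samples adjustment therefore cannot be less precise than raw change, and the two are equally precise when r = k. Any further gain from parity is not counted here.

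**4. Which k is plausible?** Section 6 restricts entry to a cervix of at most 3 cm and at most 60% effaced. That truncates two Bishop components at baseline but not at follow-up, so k below 1 is more plausible than k = 1. The documents do not give its value.

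**The case against.** **The SAP may settle this.** Section 14 says that the SAP will describe the analysis in more detail. That softens the gap without closing it. The promise is general, while the only method explicitly deferred among the secondary outcomes is the one for time to active labour. For the Bishop score a descriptive method is stated.

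**The contrast with the other outcomes is uneven.** For time to 6 cm the plan names survival methods but no specific estimate or test. This stands: the clear contrast is with the delivery rates and satisfaction.

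**Formal analysis brings its own problems.** A complete-case model drops women with no 12-hour score, for example those already delivered, and so selects on a post-randomisation event. The score is also a clinician's examination in an open-label trial. Both points stand and shape the fix. By-arm summaries have the same problems.

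A reader might also infer stronger claims that the documents do not support:

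- *That the baseline score is ignored.* It is not, because change from baseline subtracts it. What is missing is adjustment for it as a covariate.
- *That no comparative statement will be possible.* If the by-arm summaries give n, mean and SD, they yield a crude difference and CI. What is missing is prespecification.
- *That this endpoint isolates the device from later treatment.* Section 4 allows removal before 12 hours for several reasons, and expulsion can also occur. Oxytocin or prostaglandins may follow either. Some women may have received these agents, or delivered, before the 12-hour score.
- *That adjustment cuts variance by 20% to 40%.* That is the k = 1 row only, which the entry limits make doubtful.

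**Conclusion.** The point holds as a minor improvement. A listed comparative secondary outcome has no planned between-arm estimate or CI and no covariate adjustment for a baseline score that is already collected.

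The main benefit is a prespecified difference with an interval: half-width 0.205 × SD at 182 per arm, or 0.31 to 0.62 points for an assumed SD of 1.5 to 3. The precision gain from adjustment is secondary and uncertain. For r of 0.2 to 0.6, variance falls by 20% to 40% if k = 1, and by about 1% to 21% if k is 0.5 to 0.7. SD, r and k are all assumptions.

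The primary endpoint, its decision rule and the sample size are unaffected.

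**What to change.** Replace the Bishop sentence in Section 14 with:

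> The Bishop score 12 hours after intervention will be compared between arms by ANCOVA with treatment arm, admission Bishop score and parity as terms. The adjusted Dilapan-S minus Foley mean difference will be reported with its 95% two-sided CI. Raw scores and changes will be tabulated by arm.

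Add three statements:

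- The analysis population. Section 14 names none for this outcome.
- The number of women in each arm without a 12-hour score, with reasons, and a sensitivity analysis that includes them. One option is a rank-based comparison with a rule, fixed in advance, for women who have already delivered.
- A caveat that the score was assessed open-label and that some scores may follow oxytocin or prostaglandins.

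The cost is a few SAP sentences and one extra model, plus the sensitivity analysis. Both scores and parity are already on the data list, so no new data item and no additional women are needed.
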